1. Abstract: The goal of the current project is to enhance understanding of the neural mechanisms associated with the pain experience in youth with functional abdominal pain disorders (FAPD), which is the most common and debilitating presentation of FAPD. This study will examine the neural mechanisms associated with pain induction and diminished attentional regulation during pain in FAPD. Findings from pilot studies indicate that increased anxiety in FAPD is associated with higher pain-related impairment, and that anxiety may adversely impact response to a cognitive behavioral intervention for pain. While pain outcomes improve when anxiety is also addressed in treatment for FAPD, a sizable portion fail to respond to currently available interventions. Further, the PI found that induced pain in FAPD is associated with changes in regional brain activity and functional connectivity between brain regions that are implicated in chronic pain. It is crucial to better understand the neural mechanisms which may place youth with FAPD at risk for poorer outcomes in order to ultimately develop more effective treatments. In this study, neural mechanisms of response to a pain symptom provocation task in youth with FAPD will be compared to healthy controls. The impact of anxiety levels will also be explored. This study will also examine neural mechanisms associated with disrupted attentional regulation during pain induction in youth with FAPD.

2. Purpose of Study: The *objectives* of this study are to identify neural mechanisms of increased pain in pediatric FAPD and examine mechanisms of disrupted attention in the presence of induced pain. The *overarching goal* is to determine whether youth with FAPD process pain differently than healthy youth and to identify the brain areas involved.

2.A. Specific Aims:

Aim 1. Identify neural mechanisms during pain induction using the water load symptom provocation task (WL-SPT) in youth with FAPD vs HC. **H1a.** Brain regions associated with attentional, affective, and visceral afferent processing will show greater activations after the WL-SPT in youth with FAPD vs HC. **H1b.** AMY-PFC functional connectivity will be enhanced following WL-SPT in the FAPD group vs HC. **H1c.** Increased brain activity and functional connectivity will correspond to higher pain in FAPD.

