8.B. Data Management: All data will be identified with ID numbers exclusively and kept in locked files in a space in [name] research laboratory that is designated specifically for the purposes of this project. All deidentified data (with the exception of fMRI data that will be stored on a separate, secure server) will be entered into a Redcap database on a network devoted solely to the research activities of BMCP. Electronic data stored on CCHMC's network is backed up nightly. The server is maintained and all backups are conducted by the Division of Information Services. Access to data and participant identities will be limited to [name] and key study personnel (e.g., mentoring team, research coordinator, fellow). The fMRI data will also be stored on a secure server, backed up nightly, which will only be accessible to study staff.

9. Methods:

9.A. Study Design: Youth with FAPD and healthy controls will be recruited (see recruitment sections and participant inclusion/exclusion criteria below)

Pilot testing phase: To determine initial feasibility, up to 5 HC and 5 youth with FAPD who otherwise would not meet the broader fMRI safety criteria (e.g., agoraphobia, braces) will be recruited. For these participants, the cognitive task with and without WL-SPT will be conducted outside of the scanner. Measures of pain intensity, pain unpleasantness, and state anxiety will be obtained throughout. We will compare differences in RT in youth with and without FAPD after the WL-SPT. The total time of this visit is expected to be 1.5 hours.

Active study phase: At the neuroimaging visit, all children will receive an fMRI scan, where they will complete some preliminary scans and then a cognitive task, and then be removed

from the scanner to complete a water loading symptom provocation task (WL-SPT), a non-invasive validated procedure in pediatric FAPD populations to induce abdominal sensations similar to those experienced during an FAPD episode (see Walker et al., 2006). After the WL-SPT task, they will resume the fMRI scan and will complete additional scans including the cognitive task they completed earlier to assess for diminished attentional regulation. Measures of pain intensity, pain unpleasantness, and state anxiety will be obtained throughout. The duration of the brain imaging visit is two hours, with the majority of that time spent in the scanner.

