9.B. Participants: A total of 10 youth will be recruited to pilot test the procedures outside of the scanner (up to 5 HC and up to 5 with FAPD). Then, for the active part of the study, a total of 50 participants will be recruited (25 with FAPD and 25 HC). Children with FAPD will be recruited based on the presence of an FAPD diagnosis (see inclusion/exclusion criteria below). Healthy controls (HC) will not have an FAPD diagnosis.

Inclusion Criteria:

- a. Children (boys and girls) between 11-16 years of age and their parent/primary caregiver.
- b. Meets criteria for one of two study groups:
 - FAPD: based on physician diagnosis of FAPD confirmed by a validated Rome IV measure.
 - HC: based on a rule out of an FAPD diagnosis (using the Rome IV measure).

We will recruit approximately 50% of HCs with and without clinical levels of anxiety (e.g., SCARED cut-off score greater than or equal to 25) to match the anxiety levels anticipated in the FAPD group.

- c. Sufficient English language ability necessary to complete study measures and protocol

Exclusion Criteria

- a. Children with significant medical condition(s) with an identifiable organic cause including those that may account for abdominal pain symptoms (e.g., Inflammatory Bowel Diseases such as Ulcerative Colitis and Crohn's Disease). Rationale: Children with a significant medical condition may impact the study results. Further, youth with organic conditions that include abdominal pain may not meet criteria for FAPD even if they present with similar symptoms.
- b. Children with a documented developmental delay, autism spectrum disorder, a previously diagnosed thought disorder (i.e., psychosis), or bipolar disorder will be excluded. Rationale: These comorbidities may confound the study aims by impacting the dependent measures.
- c. Significant visual, hearing, or speech impairment. Rationale: Children will be excluded if they are not able to see the testing stimuli, hear the test examiner, or respond verbally to the test examiner, even with the help of corrective or assistive devices (e.g., glasses, hearing aids).
- d. Organic brain injury. Rationale: Children must not have a history of epilepsy, a head trauma associated with a loss of consciousness, or any other organic disorder since these conditions could possibly affect brain function and cognition and interfere with study results.
- e. *Other exclusionary criteria specific to the fMRI component of the study:

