9.C.1. Recruitment and Screening: Eligible participants with FAPD will be identified for the study from new or existing participants seen at the outpatient pediatric GI clinics. We request a waiver of HIPPA authorization for preparatory research to identify potential participants based on inclusion/exclusion criteria. We are also requesting a waiver of documentation of consent for the screening process. Participants will be assured that their usual medical care will not be affected based upon whether or not they choose to participate. HCs will be enrolled using a multi-pronged recruitment approach potentially including flyers placed in the community and around CCHMC, a CCHMC database of healthy individuals willing to participate in research, and online advertisements (e.g., CCHMC email blasts). HC who express interest will be contacted by research staff via telephone. Research staff will describe the study, answer questions, and complete a brief (IRB approved) phone screening with the caregiver and child to assess for FAPD, anxiety, and MRI eligibility. If potentially eligible, HC will be invited to complete a neuroimaging visit where they will be formally consented by research staff and complete the formal study measures.

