For both youth with FAPD and those that are HC, written consent from the primary caregiver and written assent from the child will be obtained. All participants will be notified that screening is necessary and study entry is not guaranteed at this point. If the child is not eligible and the family is interested in the child receiving mental health services, contact information for the psychology service at CCHMC will be provided. Following informed consent and child assent, the following screening measures will be completed with the child by a member of the research staff: a measure of FAPD symptoms/diagnosis, clinical anxiety, and questions regarding fMRI eligibility. This process takes ~10 minutes. Study staff will complete the ROME IV FAPD diagnostic checklist with the participant's gastroenterology provider to ensure that the child meets FAPD criteria. Some patients will have already completed the SCARED at their medical visit as a part of clinical practice. For those patients, SCARED data will be obtained through EPIC. The participants and families will answer questions to ensure the child can safely enter the scanner and undergo fMRI and study procedures. Screening may take place after the clinic visit. If youth are determined to be eligible, they will be invited to participate in an fMRI visit.

9.C.2. Assessments: Qualifying participants and their respective caregivers will be scheduled to complete an in-person neuroimaging visit. Next, participants will enter the MRI and perform a

cognitive task to enhance attention to pain. *Performance is measured by reaction time.* This task was previously used in brain imaging studies of healthy adults to understand the effects of pain induction, and captures a “pain-attentive” group (i.e., reaction times >100 ms) (38) thought to categorize chronic pain conditions such as FAPD. This task involves judgements on groups of digits to indicate 1) the most frequently listed digit ignoring the value, and 2) the largest digit ignoring the frequency. Similar tasks were used in a pain study of healthy adults (50), and with healthy children (without pain) with evidence of brain activations in expected areas (56).

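### Does a control group defined only by the absence of FAPD, with no rule on other chronic pain, undermine the FAPD versus healthy control contrast?

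*Combined protocol and SAP*

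**What the plan says.** Section 2 gives the overarching goal: to "determine whether youth with FAPD process pain differently than healthy youth". Section 9.B then fixes who counts as a control: "HC: based on a rule out of an FAPD diagnosis (using the Rome IV measure"). The same section adds that controls will have no FAPD diagnosis, and that about half will be recruited with clinical anxiety "to match the anxiety levels anticipated in the FAPD group".

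The exclusions apply to both groups. Exclusion (a) covers "Children with significant medical condition(s) with an identifiable organic cause", and exclusion (d) covers organic brain injury and other organic disorder. The rest concern developmental and psychiatric diagnoses, sensory impairment and MRI safety.

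Section 9.C.1 summarises the control phone screen as a "phone screening with the caregiver and child to assess for FAPD, anxiety, and MRI eligibility". The screening measures after consent are "a measure of FAPD symptoms/diagnosis, clinical anxiety, and questions regarding fMRI eligibility". One possible source of controls is a hospital "database of healthy individuals willing to participate in research"; flyers and online advertisements are others. Section 9.D also lists the past-week pain rating and the Functional Disability Inventory under its screening heading, with no limit set for controls. It lists pain duration, location and medication under Pain History at the scan visit.

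**The concern.** A child with migraine or another functional pain condition outside the abdomen meets every written criterion for a healthy control. That sits badly with the stated goal. It also sits badly with Section 9.F, where the between-group imaging power rests on data comparing youth with migraine against healthy controls and reporting moderate to large differences. The protocol appears to treat migraine as something other than healthy in one place and to admit it as healthy in another.

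If such controls reacted to the water load partly as FAPD youth do, the contrasts under H1a (regional activation) and H1b (amygdala–prefrontal connectivity) would shrink, and a null result would be harder to read. With about 20 analysable controls, each child is 5% of the group, so a few could matter.

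**Working it through.** **Which contrast the text defines.** Section 2 states a goal in general words; Section 9.B is the rule by which children are enrolled. Two other places agree with 9.B. The pilot phase in 9.A says "We will compare differences in RT in youth with and without FAPD after the WL-SPT", which is FAPD against non-FAPD. The anxiety rule in 9.B deliberately brings clinically anxious children into the control group, so controls were not meant to be free of every related condition. Other functional pain is barred in neither group, so the rule is symmetric.

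**What the imaging outcome is.** Section 9.E identifies pain-related activation by comparing scans before and after water loading within each child, then contrasts that change between groups. A stable difference between a child with migraine and a pain-free child largely cancels. What remains is whether the *change* after an abdominal stimulus differs, and no section gives data on that. The migraine data in 9.F come with no stated task, region or number and do not describe a water load.

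**Illustration of size.** This can be done only for pain ratings, because the documents give no numeric imaging effect.

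Inputs from 9.F: d = 0.73, R² = 0.35, five covariates, 20 per group. Assumed, because the documents do not give them:

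- p, the share of controls affected;
- r, their response as a fraction of the FAPD shift (0 = like pain-free controls, 1 = like FAPD youth).

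Formulae:

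- Diluted effect = 0.73 × (1 − p·r).
- Noncentrality = effect / √(1 − 0.35) / √(1/n₁ + 1/n₂), with df = n₁ + n₂ − 7, two-sided 0.05. The extra variance from mixing two kinds of control is ignored.

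The plan's own figure first. With p = 0, 0.73/√0.65 = 0.905 and 0.905/√(2/20) = 2.86 on 33 df, giving power 0.794. Section 9.F claims more than 0.80 at d = 0.55; this model gives 0.553 there. That is a separate matter and does not bear on the control definition.

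| Controls affected | r = 1 | r = 0.5 | r = 0.25 | r = 0 | r = −0.25 | Affected controls excluded |
|---|---|---|---|---|---|---|
| 5% (1 of 20) | 0.75 | 0.77 | 0.78 | 0.79 | 0.80 | 0.78 (20 v 19) |
| 10% | 0.71 | 0.75 | 0.77 | 0.79 | 0.81 | 0.77 (20 v 18) |
| 20% | 0.60 | 0.71 | 0.75 | 0.79 | 0.83 | 0.74 (20 v 16) |

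Example: p = 0.20, r = 0.5 gives 0.73 × 0.90 = 0.657 and power 0.706.

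Excluding affected controls restores d to 0.73 but costs children. It breaks even at r of about 0.28, 0.29 and 0.31 in the three rows. Below that it loses power: at r = 0 the loss is 0.01, 0.02 and 0.05. With 25 per group and 20% affected, power is 0.88 undiluted, 0.71 at r = 1 and 0.84 after exclusion, with break-even at about 0.30.

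A simulation with five random covariates and the true mixture (10,000 runs, 20 per group, 20% affected) gives lower levels in the same order: 0.74 undiluted, 0.64 at r = 0.5, 0.52 at r = 1 and 0.68 after exclusion.

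**What each possible change would buy.**

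- *Bar other pain in controls only.* The FAPD group may still carry migraine or other functional pain, so the contrast would mix FAPD with pain conditions in general. It becomes less specific to FAPD, and recruitment slows.
- *Add an analysis that excludes affected controls.* This gains power only if r exceeds about 0.3, and no section gives a reason to expect that.
- *State that the contrast is FAPD versus non-FAPD, or tabulate other pain.* This writes down what 9.B already implies and alters no estimate.

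**The case for a change.** The strongest case for acting is that the two descriptions of the comparator differ, that the protocol's own power data separate migraine from healthy, and that the exposure may go unrecorded. Baseline pain appears as a covariate only in the power assumptions. Pain History is offered as a possible covariate and is not an entry check. Section 4 describes the visit's pain content as abdominal. The healthy-volunteer database is only one possible source of controls. If other pain is not recorded at enrolment, a null result cannot later be examined for it, and a screening question would cost little.

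Part of this stands: no rule on non-abdominal pain in controls is stated, and the past-week pain rating and disability inventory do not identify the type of pain. But these measures sit under the screening heading in 9.D, and the note that they may come from the medical record for FAPD patients suggests they are not confined to that group. With Pain History, they let an analyst flag controls with notable pain and describe both groups. The phone script is not in the documents, so the absence of a general pain question is inferred from a one-line summary. The migraine argument does not carry over, because those data say nothing about response to a water load.

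**Conclusion.** No change follows. The control definition in 9.B is narrower than the word healthy suggests, but it is a usable and symmetric definition of non-FAPD controls, and the documents do not show that it biases the within-child water-load contrast in either direction. On pain ratings, under assumed shares of 10% to 20%, the effect on power runs from a fall of 0.09 to 0.19 (r = 1), through nil (r = 0), to a rise of 0.02 to 0.04 (r = −0.25), against 0.79 undiluted. For the imaging hypotheses no size can be given. These figures rest on d = 0.73, R² = 0.35 and 20 per group from 9.F, and on values of p and r that the documents do not supply.

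The choice between non-FAPD and pain-free controls is a trade-off between specificity to FAPD and a cleaner reference group. Analysts can describe other pain in both groups, so far as the measures already listed capture it, and word the comparator accordingly in the report. The judgement would change if there were evidence that controls with other pain respond to the water load at well over 0.3 of the FAPD shift and make up a material share of the group.

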Imaging protocol. Brain images will be acquired via a 2015 model Philips 3T Ingenia MRI system using a 32-channel head coil. Pain intensity/unpleasantness and state anxiety ratings will be acquired after each sequence. Imaging will occur using block design, and will include sequences obtained at rest, and in the presence/absence of the cognitive task (with and without water loading). The pilot testing phase will allow for refinement of a neuroimaging protocol for the active study.

9.C.3. Payment: Families will receive payment for this study in the form of a reloadable debit card (ClinCard). A handout will be given to families that will explain how to use the card. Because families are being paid for their participation, CCHMC is required by the Internal Revenue Service (IRS) to collect and use the participant’s social security number (SSN) or taxpayer identification number (TIN) to track the amount of money that they are paid. Families will need to complete a Federal W-9 form for this income tax reporting. This form requires the participant’s Social Security number. This form will be given to the CCHMC business office. It will not be kept as part of the participant’s study chart. Subjects will receive a \$25 incentive for their screening visit. Participants recruited to participate in the pilot testing phase (no MRI) will be compensated \$50. We will reimburse families and participants who are recruited as part of the active research project for the visit that includes the MRI an additional \$100.

9.D. Measures: *Standardized, psychometrically validated* instruments used in prior pediatric pain studies will be used. These measures will be administered using the REDCap data capture platform.

Screening:

FAPD questionnaire (57). Measure to confirm diagnosis of FAPD based on Rome IV diagnostic criteria.

Screen for Child Anxiety Related Disorders (SCARED) (58, 59). A 41-item measure of anxiety over the past 3 months for children ages ≥ 8 (60). Scores ≥ 25 = clinical anxiety cut-off. The SCARED was validated in pediatric pain (61), and >50% of children with FAPD experience clinical anxiety, which is related to higher pain/disability (9). If this measure is not obtained clinically, it will be administered as part of the research protocol.

MRI Safety and Screening. Research staff to determine if patient can safely complete fMRI protocol.

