Numeric Rating Scale (NRS) (62) for pain. Average, highest, and lowest pain levels in the past week will also be assessed.

Functional Disability Inventory (FDI) (63). 15-item measure of physical/daily function in last few days. This measure has been validated in pediatric chronic pain (64) and used in pediatric FAPD samples (9,24).

Note. For patients with FAPD, some measures (SCARED, FDI, NRS) may be available as part of the participants clinical screening. If so, they will be obtained from the EMR.

Measures administered during fMRI visit:

Pain History. Family socio-demographic factors (e.g., age, parent employment), and child pain information (e.g., duration, location, medication) will be obtained (available as covariates).

Pain Intensity/Unpleasantness via the Visual Analog Scale (VAS) (65, 66). Scale with the words “no pain intensity/unpleasantness” and “worst pain intensity/unpleasantness”, validated for children ≥ 8 years. Large effects after the WL-SPT have been observed (67).

State Anxiety (VAS) (68). 0-10 self-report of how anxious the child is feeling in the moment.

Fullness Rating Scale (67). Youth will be asked to indicate how full they felt after water ingestion by selecting from images representing different levels of fullness, from empty to full.

Pain Catastrophizing Scale for Children (69). A valid measure of maladaptive beliefs about pain and feelings experienced when in pain.

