9.E. Data Analysis: For the fMRI data, image processing and data analysis will be accomplished using FSL (70). Each subject’s functional images will be registered to their structural data using a six-parameter linear 3-D transformation and then nonlinearly warped to standard space (MNI152) (71-73). The aCompCor approach will be used to preprocess BOLD data for functional connectivity and psychophysiological interaction analyses (74). This process minimizes the impact of global signal changes as well as signal changes induced by movement and other sources of noise. Analyses of data will be accomplished via mixed effects ANOVAs. Pain-related activation will be identified in images by comparing pre vs. post water loading data within subjects. These findings will then be contrasted across FAPD and HC groups. Multiple regression analyses will be used to examine if the changes in brain regions are related to the pain intensity/unpleasantness/anxiety. Next, changes in pain-related brain activation and functional connectivity *during* the cognitive task following the WL-SPT will be examined. There will also be a wealth of data available for exploratory analysis. Such analyses may include examining resting state FAPD data vs. HC data and exploring groups by anxiety level.

9.F. Sample Size: Analyses were powered to address pain intensity/unpleasantness differences measured during the pilot WL-SPT study (67). A Monte Carlo simulation was performed to obtain a power estimate for the analyses under the following assumptions: 1) equivalent sample sizes for the two groups, 2) covariates (age, gender, ethnicity, SES, baseline pain) will explain ($R^2 = 0.35$) 35% of the variance, and 3) an effect size difference between FAPD and HC of $d = 0.73$ is observed. Monte Carlo simulation results showed power >0.80 to detect a $d = 0.55$ difference if 20 per group (total $N = 40$) are available for analysis after proper handling of missing data. Additional power calculations using

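### SCARED, FDI and NRS may come from clinic records in FAPD but are collected at the scan visit in controls, so these three scores are not comparable in time or setting

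*Combined protocol and SAP*

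**What the plan says.** Section 9.D lists SCARED, NRS and FDI as screening measures and adds a note for one group only: "For patients with FAPD, some measures (SCARED, FDI, NRS) may be available as part of the participants clinical screening". The next sentence gives the rule: "If so, they will be obtained from the EMR". Section 9.C.1 repeats it for SCARED in patients who completed that scale at a medical visit: "For those patients, SCARED data will be obtained through EPIC". Research administration is the fallback for SCARED: "If this measure is not obtained clinically, it will be administered as part of the research protocol".

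Controls have no record route. Section 9.C.1 has research staff contact them by telephone for a "phone screening with the caregiver and child to assess for FAPD, anxiety, and MRI eligibility". Those who appear eligible give formal consent and complete the formal measures at the neuroimaging visit.

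On recall periods, Section 9.D gives three months for SCARED and the last few days for FDI. For NRS it says: "Average, highest, and lowest pain levels in the past week will also be assessed".

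Anxiety level is used in two places. Section 9.B recruits about half of the controls at or above the SCARED cut-off of 25, "to match the anxiety levels anticipated in the FAPD group". Section 9.E names, as a possible exploratory analysis, "exploring groups by anxiety level", and the abstract also says the impact of anxiety will be explored.

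**The concern.** The source of a score depends on group. An FAPD child may contribute a value recorded in a clinic at some earlier date, while a control contributes one collected by research staff on the day of the scan. A difference in SCARED, FDI or NRS between groups then mixes the condition with the occasion and setting of measurement. Only some FAPD children will have record scores, so the same mixture exists inside the FAPD group.

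The plan states this as a rule, so the issue is more than missing detail. The plan gives no maximum age for a record score, no repeat at the scan visit, no recording of source and date, and no adjustment in analysis. FAPD participants may be established clinic patients as well as new ones (Section 9.C.1), so an old score is possible.

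At stake are the check that the groups are balanced on anxiety, the exploratory anxiety analysis, the description of the groups on pain and disability, and possibly one covariate. A score that was not collected near the scan cannot be recovered afterwards.

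**Working it through.** The plan states no figure on this point, so there is none to reproduce. The check sets the provisions side by side and then illustrates size under stated assumptions.

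**1. Source and timing by group (Sections 9.C.1 and 9.D)**

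| | FAPD | Controls |
|---|---|---|
| SCARED | Record if present, otherwise research administration | Anxiety asked about by telephone; formal measures at the neuroimaging visit |
| FDI, NRS | Record if present | Formal measures at the neuroimaging visit |
| Maximum age of score | None stated | Not applicable to same-day scores |
| Repeat at scan visit | None: all three are absent from the fMRI-visit list | Not needed |
| VAS pain and state anxiety | At the scan visit | At the scan visit |

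**2. How much a gap matters for each scale.** For recall window w and gap g between the clinic score and the scan, the share of the window that overlaps the window before the scan is max(0, (w − g)/w).
- NRS, w = 7 days: at g = 7 days, (7 − 7)/7 = 0.
- FDI, w = a few days: zero once the gap exceeds a few days.
- SCARED, w = about 90 days: at g = 7 days, (90 − 7)/90 = 92%. It reaches zero only at a gap of about three months.

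So NRS and FDI are the most exposed, and SCARED much less unless the record score is old.

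**3. Where the scores are used.**
- The control quota in Section 9.B is fixed at about 50% on anticipated FAPD anxiety. Observed FAPD scores do not move it; they enter only a later check that balance was achieved.
- The analysis by anxiety level in Section 9.E is optional and exploratory.
- Section 9.E names neither NRS nor FDI.
- Section 9.F lists baseline pain as a covariate without naming the instrument. Section 4 has baseline symptoms and VAS pain reported at the fMRI visit, so VAS is the more natural reading, but NRS is not ruled out.

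**4. Illustrative size for a group comparison of one of these scores.** Let q be the share of FAPD scores taken from records and s the occasion or setting shift in SD units. Both are assumed; neither is in the documents. With n = 20 per group (Section 9.F) and two-sided 5%:
- Bias = q × s.
- δ = q × s × √(20/2).
- Rejection rate with no true difference = 1 − Φ(1.96 − δ) + Φ(−1.96 − δ).

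| q | s | Bias (SD) | δ | Rejection rate |
|---|---|---|---|---|
| 0.25 | 0.1 | 0.025 | 0.08 | 5.1% |
| 0.5 | 0.2 | 0.10 | 0.32 | 6.2% |
| 0.5 | 0.5 | 0.25 | 0.79 | 12.4% |
| 1 | 0.2 | 0.20 | 0.63 | 9.7% |
| 1 | 0.5 | 0.50 | 1.58 | 35.3% |

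**5. Illustrative cost if baseline pain is the NRS.** Section 9.F assumes that the covariates explain R² = 0.35. Suppose out-of-date scores reduce this to 0.20 (assumed). For a simple adjusted two-group comparison, power ≈ Φ(d/√(1 − R²) × √(20/2) − 1.96). At d = 0.73:
- R² = 0.35: 0.73/0.806 × 3.162 − 1.96 = 0.90, power 0.82.
- R² = 0.20: 0.73/0.894 × 3.162 − 1.96 = 0.62, power 0.73.

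This is a normal approximation. It is not the plan's Monte Carlo model, which is not described.

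**The case against.** The strongest reply is that little of importance depends on these scores. VAS pain intensity, unpleasantness and state anxiety are collected at the scan visit in both groups and after each sequence, and the regressions in Section 9.E name quantities that match those ratings. The control quota is fixed in advance, the anxiety-level analysis is optional, and SCARED looks back three months. All of this stands and limits the reach of the point.

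A second reply is that the record rule is not the only source of the timing difference. Sections 4 and 9.C.1 place FAPD screening after a clinic visit, so a research-administered FAPD score may also be taken close to that visit. That is fair, but it argues for a common collection point, not for leaving the rule as it is.

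A third reply is that the direction of bias is unknown. A reader might infer that clinic scores overstate FAPD anxiety and pain because children attend when symptoms are worse. The documents say nothing of the kind. A reader might also try to size the effect by regression to the mean, multiplying one minus a reliability by the elevation at the clinic visit. No reliability is given, and that formula describes deviation from a population mean, not from a child's own usual level. Neither inference is relied on here. The scores remain non-comparable whichever way the shift runs.

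**Conclusion.** The point holds as a minor one. SCARED, FDI and NRS are collected under different timing and setting rules in the two groups, and unevenly within FAPD, with no stated safeguard. The scores exposed are those used for the anxiety-balance check, the exploratory analysis by anxiety level, group descriptions of pain and disability, and the baseline-pain covariate if that is the NRS.

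The documents fix neither direction nor size. Under the assumed inputs above, the effect runs from negligible (5.1% rejection when a quarter of FAPD scores come from records with a 0.1 SD shift) to substantial (35.3% when all do, with a 0.5 SD shift).

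Two stronger readings are tempting and unsupported. One is that the rule contaminates the main pain comparison or the imaging contrasts: the VAS ratings and scans are obtained at the same visit in both groups. The other is that it distorts recruitment of anxious controls: that quota rests on anticipated, not observed, FAPD anxiety.

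**What to change.** Use record values for screening only. Administer SCARED, FDI and NRS to both groups at the fMRI visit, before the scan, and use those scores for the balance check, any covariate use and the anxiety analyses. State in Section 9.F which instrument supplies baseline pain.

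The cost is a few minutes of questionnaires, falling on FAPD children because controls already complete the formal measures at that visit: 41 SCARED items, 15 FDI items and 3 NRS ratings, 59 in all. REDCap is already in use and no extra staff are needed. The drawback is pressure on a visit of about 2 hours, since Section 4 already allots about 15 minutes (possibly 15 + 15) plus about 100 minutes in the scanner.

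If that time cannot be found, the minimum is a stated maximum interval between a record score and the scan, with the source and date of every score recorded so that sensitivity to them can be examined.
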